ICMJE	International Committee of Medical Journal Editors
ID	Identifier
IMP	Investigational medicinal product
IND	Investigational New Drug
IRB	Institutional review board
IRE	Immediately reportable event
ITC	Itraconazole
K ₂ EDTA	Dipotassium ethylenediaminetetraacetic acid
MedDRA	Medical Dictionary for Regulatory Activities
NIMP	Noninvestigational medicinal product

CCI

PK	Pharmacokinetic
PQC	Product quality complaint
q12h	Every 12 hours
QD	Once daily
QTc	Corrected QT interval
QTcF	QT interval corrected for heart rate using Fridericia's formula
RBC	Red blood cell
RNA	Ribonucleic acid
SAE	Serious adverse event
SoA	Schedule of assessments
t _{1/2,z}	Terminal-phase elimination half-life
TB	Tuberculosis
TEAE	Treatment-emergent adverse event
t _{max}	Time to maximum (peak) plasma concentration
ULN	Upper limit of normal
US or USA	United States or United States of America
USPI	United States Prescribing Information
WBC	White blood cell

1 Protocol Summary

1.1 Synopsis

Name of Sponsor: Otsuka Pharmaceutical Development & Commercialization, Inc.

Name of Investigational Medicinal Product: OPC-167832

Protocol No.: 323-201-00007

IND No.: 129303

Protocol Title: A Phase 1, Single-center, Two-part, Open-label, Pharmacokinetic Trial to Assess the Potential for Cytochrome P450 3A Mediated Drug-drug Interactions with Orally Administered OPC-167832 Tablets in Healthy Adult Subjects

Protocol Lay Person Short Title: A Study to Test the Effects of Itraconazole and Carbamazepine on OPC-167832 in Healthy Men and Women

Clinical Phase: 1

Planned Treatment/Indication: Tuberculosis

Objectives and Endpoints:

Objectives	Endpoints

Primary: To assess the potential for CYP-mediated drug-drug interactions with OPC-167832:
 
 Inhibition of OPC-167832 metabolism via CYP3A by itraconazole Induction of OPC-167832 metabolism via CYP3A by carbamazepine 	
Primary:
 
OPC-167832 PK: C_{max}, AUC_t, and AUC_{∞}

Secondary: To assess the safety and tolerability of OPC-167832 administered alone or in combination with itraconazole or carbamazepine
	
Secondary:
 
Safety: AEs, clinical laboratory tests, vital signs, physical examinations, 12-lead ECGs, and C-SSRS (Part 2 only)

AE = adverse event; AUC_{∞} = area under the concentration-time curve from time zero to infinity;

AUC_t = area under the concentration-time curve calculated to the last observable concentration at

time t; C_{max} = maximum (peak) plasma concentration of the drug; C-SSRS = Columbia-Suicide

Severity Rating Scale; CYP = cytochrome P450; ECG = electrocardiogram; PK = pharmacokinetics.

Trial Design: This is a single-center, 2-part, open-label drug-drug interaction (DDI) trial in healthy adult subjects. Part 1 and Part 2 will have fixed sequence designs with 12 subjects in each part for a total of 24 subjects enrolled.

Following a screening period of up to 28 days, eligible subjects will enter the clinic on the day prior to the first treatment day (Day -1).

For Part 1, the impact of CYP3A inhibition on the PK of OPC-167832 will be assessed. Subjects will receive a single, 30-mg, oral dose of OPC-167832 CCI in the fasted state on Day 1 with blood collections for PK assessment of OPC-167832 from Day 1 through Day 8. On Day 8, subjects will receive 200-mg doses of itraconazole in the morning and evening (200 mg twice daily [BID]) followed by 200 mg of itraconazole administered once daily on Day 9 through Day 14 to approach steady-state conditions for itraconazole. On Day 15, a single, 30-mg, oral dose of OPC-167832 CCI will be administered concurrently with a 200-mg dose of itraconazole in the fasted state with blood collections for PK assessment of OPC-167832 from Day 15 through Day 26. Once daily 200-mg doses of itraconazole will continue to be administered on Day 16 through Day 25. Subjects will be discharged from the clinic after the PK sample on Day 26 or early termination (ET).

For Part 2, the impact of CYP3A induction on the PK of OPC-167832 will be assessed. Subjects will receive a single, 30-mg, oral dose of OPC-167832 CCI on Day 1 in the fasted state with blood collections for PK assessment of OPC-167832 from Day 1 through Day 8. On Day 8 through Day 10, subjects will receive 100 mg BID carbamazepine followed by 200 mg BID carbamazepine administration on Day 11 through Day 13 and 300 mg BID carbamazepine administration on Day 14 through Day 31. On Day 25, a 30-mg oral dose of OPC-167832 CCI will be administered concurrently with the morning 300-mg dose of carbamazepine in the fasted state with blood collections for PK assessment of OPC-167832 from Day 25 through Day 32. Subjects will be discharged from the clinic after the PK sample on Day 32 or ET.

All subjects will be contacted by phone 30 days after the last dose of OPC-167832 to assess any new or ongoing AEs and to record concomitant medications.

Trial Population: Twenty-four subjects will be enrolled, 12 subjects in each part, such that approximately 10 healthy male or female subjects complete each part.

Key Inclusion/Exclusion Criteria: Male and female subjects between the ages of 18 and 55 years (inclusive), with a body mass index (BMI) between 19 and 32 kg/m² (inclusive), who are in good health as determined by medical history, physical examination, 12-lead electrocardiogram (ECG), serum/urine chemistry, hematology, and serology tests, and who are able to provide informed consent will be considered for inclusion in the trial.

Trial Site(s): This trial will be conducted at 1 site in the United States.

Trial Intervention(s), Dose, Dosage Regimen, Treatment Duration, Formulation, Mode of Administration: OPC-167832, itraconazole, and carbamazepine will be administered orally to subjects as per the dosing schedule below. OPC-167832 CCI will be provided as 30-mg tablets, itraconazole will be administered as a 10-mg/mL oral solution, carbamazepine will be administered as the least number of tablets based on commercially available extended-release tablets (ie, 100-mg tablet, 200-mg tablet). Lower dose strengths of carbamazepine can be combined, ie, a 100-mg tablet and a 200-mg tablet should be combined to dose at 300 mg. All doses will be administered with approximately 240 mL of room temperature, still water. When itraconazole is administered, some of the 240 mL of water should be used to rinse the dosing container. All doses of OPC-167832 (administered on Days 1 and 15 in Part 1 and Days 1 and 25 in Part 2) will be administered following an overnight fast of at least 10 hours.

For Part 1, OPC-167832 and itraconazole will be administered in the morning at the same time each day. The BID dose of itraconazole on Day 8 will be administered every 12 hours (q12h). On days of serial PK sampling days (Days 1 and 15), subjects will be required to continue to fast from food for at least 4 hours following dosing of OPC-167832 and water will be restricted for 1 hour before to 2 hours after dosing of OPC-167832. Water is permitted ad libitum on all other days.

For Part 2, OPC-167832 and carbamazepine will be administered in the mornings at the same time each day and BID doses of carbamazepine will be administered q12h and at same time each evening. On days of serial PK sampling days (Days 1 and 25), subjects will be required to continue to fast from food for at least 4 hours following of OPC-167832 and water will be restricted for 1 hour before to 2 hours after dosing of OPC-167832. Water is permitted ad libitum on all other days.

Study Day	Time	Dose
PART 1		
1	morning	30 mg OPC-167832
8	morning	200 mg itraconazole
	evening	200 mg itraconazole
9 through 14	morning	Once-daily 200 mg itraconazole
15	morning	30 mg OPC-167832 and 200 mg itraconazole
16 through 25	morning	Once-daily 200 mg itraconazole
PART 2		
1	morning	30 mg OPC-167832
8 through 10	morning	100 mg carbamazepine extended release
	evening	100 mg carbamazepine extended release
11 through 13	morning	200 mg carbamazepine extended release
	evening	200 mg carbamazepine extended release
14 through 24	morning	300 mg carbamazepine extended release ^a

Study Day	Time	Dose
	evening	300 mg carbamazepine extended release ^a
25	morning	30 mg OPC-167832 and 300 mg carbamazepine extended release ^a
	evening	300 mg carbamazepine extended release ^a
26 through 31	morning	300 mg carbamazepine extended release ^a
	evening	300 mg carbamazepine extended release ^a

^aLower dose strengths of carbamazepine can be combined, ie, a 100-mg tablet and a 200-mg tablet should be combined to dose at 300 mg.

Trial Assessments: Assessments for Pharmacokinetics: blood sampling to determine the concentrations of OPC-167832, itraconazole, and carbamazepine.

CCI

Assessments for Safety: adverse events, clinical laboratory tests, 12-lead ECG, vital signs, physical examination findings, the Columbia-Suicide Severity Rating Scale (Part 2 only).

Screening/Other: Demographics, medical and medication history, serum hepatitis and human immunodeficiency virus screen, urine alcohol test, drug screen, severe acute respiratory syndrome coronavirus test, urine (and confirmatory serum, if needed) pregnancy test (for females of childbearing potential), follicle-stimulating hormone test (for postmenopausal females), and height/weight/BMI.

Independent Data Monitoring Committee: No

Statistical Methods: The trial plans to enroll 12 subjects in each treatment part to target approximately 10 completers per part. Sample size was selected assuming an intra-subject coefficient of variation for AUC of 25%, such that the point estimate of the ratio of geometric means for the PK parameters of OPC-167832 with and without coadministration of the perpetrator (itraconazole or carbamazepine) will fall within 83% and 120% of the true value with 90% confidence.

The effect of itraconazole or carbamazepine administration on the single-dose PK of OPC-167832 will be assessed using the primary PK parameters of OPC-167832: C_{max} , AUC_t , and AUC_{∞} in the presence and absence of either itraconazole or carbamazepine.

Statistical analyses will be performed using the log-transformed PK parameters. The magnitude of the DDI will be assessed by computing the ratio of the geometric means of the OPC-167832 + potentially interacting drug versus OPC-167832 alone and the corresponding 90% confidence intervals (CIs) based on the log-transformed data.

[figure not shown]
An analysis of variance will be performed on the log-transformed PK parameters C_{\max} , AUC_t , and AUC_{∞} for OPC-167832 and/or its metabolites using the MIXED procedure in SAS for each part separately. The mixed-effects linear model for each PK parameter will include treatment (OPC-167832 + potentially interacting drug [test] and OPC-167832 alone [reference]) as a fixed effect and subject as a random effect. From each analysis, mean differences between the treatments OPC-167832 + potentially interacting drug and OPC-167832 alone and the 90% CI for the differences will be derived. The antilog of the differences will then provide an estimate of the geometric mean ratios (GMR; OPC-167832 + potentially interacting drug/OPC-167832 alone), and the antilog of the confidence limits will provide the 90% CIs for the GMRs.

Trial Duration: Each subject in this trial is expected to participate in the following periods of the trial (approximate durations listed):

- Eligibility screening period: Day –28 to Day –2
- In-clinic treatment (2 dosing periods):
 - Part 1: Day –1 to Day 26 days (27 days)
 - OR
 - Part 2: Day –1 to Day 32 (33 days)
- Safety follow-up phone call: 30 (+ 2) days after the last dose of OPC-167832 (eg, Day 45 [+ 2 days] for Part 1 and Day 55 [+ 2 days] for Part 2 for trial completers).

The trial start is defined as the date the first subject signs their informed consent form. Overall, the trial duration, from signing of the first subject's informed consent form to the last subject's final assessment, is expected to be approximately 11 weeks for Part 1 and approximately 12 weeks for Part 2.

1.2 Schema

CBZ = carbamazepine; ITC = itraconazole.

Figure 1.2-1 Trial Design Schematic

1.3 Schedule of Assessments

Table 1.3-1 Schedule of Assessments - Part 1															
Period	Screening		Treatment											Follow-up Phone Call 30 (+2) days after last dose of OPC-167832	Notes
Visit	Screening	Check-in	Period 1			Period 2									
Trial Day	-28 to -2	-1	1	2	3 to 7	8	9 to 12	13	14	15	16	17 to 25	26 End-of-Trial or ET		
ENTRANCE/HISTORY															
Informed Consent	X														Section 10.1.2
Demographics	X														Section 5.1
Inclusion/Exclusion Criteria	X	X													Section 5.2
Medical History	X														
Height	X														Section 8.5.2
Body Weight	X	X											X		Section 8.5.2
Body Mass Index	X	X													Section 8.5.2
Serology (HIV, HBsAg, anti-HCV)	X														Section 10.2
Urine alcohol and urine drug screen	X	X													Section 10.2
Urine pregnancy test (for FOCBP)	X	X											X		Section 10.3
FSH (for postmenopausal females)	X														Section 10.2
TRIAL RESIDENCY															
Check-in to trial site clinic		X													
Discharge from Clinic													X		
SAFETY															
Adverse Events	X	X	X	X	X	X	X	X	X	X	X	X	X	X	Section 8.6.1
Physical Examination ^a	X	X								X			X		Section 8.5.2

Table 1.3-1 Schedule of Assessments - Part 1															
Period	Screening		Treatment											Follow-up Phone Call 30 (+2) days after last dose of OPC-167832	Notes
Visit	Screening	Check-in	Period 1			Period 2									
Trial Day	-28 to -2	-1	1	2	3 to 7	8	9 to 12	13	14	15	16	17 to 25	26 End-of-Trial or ET		
Vital Signs ^b	X	X	X	X						X	X		X		Section 8.5.3
Concomitant Medications	X	X	X	X	X	X	X	X	X	X	X	X	X	X	Section 6.5
12-Lead ECG ^c	X	X	X	X						X	X		X		Section 8.5.4
Laboratory Tests (hematology, serum chemistry, and urinalysis [with cell count])	X	X	X	X						X	X		X		Section 8.5.1
IMP ADMINISTRATION															
OPC-167832			X							X					Section 6.1
Itraconazole ^d						X	X	X	X	X	X	X			Section 6.1
PHARMACOKINETICS															
Blood Samples for OPC-167832 PK ^e			X	X	X	X				X	X	X	X		Section 8.2.1
Blood Samples for Itraconazole PK ^f								X	X	X					Section 8.2.1
OTHER PROCEDURES															
Medication Compliance Evaluation			X			X	X	X	X	X	X	X			Section 6.4

anti-HCV = hepatitis C antibodies; FOCBP = females of childbearing potential; FSH = follicle-stimulating hormone; HBsAg = hepatitis B surface antigen; HIV = human immunodeficiency virus antibodies; .

^a Complete physical examinations will be performed at screening, predose on Day 15, and prior to discharge or at ET. A targeted physical examination will be completed at check-in and at any time per the investigator's discretion.

^bVital signs will be measured at screening, on Day –1, predose on Day 1 and Day 15, 24 hours after OPC-167832 administration (Day 2 and Day 16), and prior to discharge on Day 26 or at ET.

^cTwelve-lead ECGs will be performed at screening, on Day –1, predose on Day 1, 3 hours after OPC-167832 administration on Day 1, and 24 hours (Day 2) after OPC-167832 administration on Day 1, predose Day 15, 3 hours after OPC-167832 administration on Day 15, and 24 hours (Day 16) after OPC-167832 administration on Day 15, and prior to discharge on Day 26 or at ET.

^dSubjects will receive 200 mg itraconazole in the morning and evening on Day 8 and 200 mg itraconazole in the morning on Day 9 through Day 25.

^eBlood samples for OPC-167832 PK will be collected predose Day 1 and at 1, 2, 3, 4, 8, 12, 24 (Day 2), 36, 48 (Day 3), 72 (Day 4), 96 (Day 5), 120 (Day 6), 144 (Day 7), 168 (Day 8) hours postdose; predose Day 15 and at 1, 2, 3, 4, 8, 12, 24 (Day 16), 36, 48 (Day 17), 72 (Day 18), 96 (Day 19), 120 (Day 20), 144 (Day 21), 168 (Day 22), 192 (Day 23), 216 (Day 24), 240 (Day 25), 264 (Day 26) hours postdose or at ET.

^fBlood samples for itraconazole and hydroxy-itraconazole PK will be collected predose and at 2.5 hours postdose on Days 13, 14, and 15.

^gCollected predose.

Table 1.3-2 Schedule of Assessments - Part 2																
Period	Screening		Treatment												Follow-up Phone Call 30 (+2) days after last dose of OPC- 167832	Notes
Visit	Screening	Check-in	Period 1			Period 2										
Trial Day	-28 to -2	-1	1	2	3 to 7	8	9 and 10	11 to 13	14 to 22	23 and 24	25	26	27 to 31	32 End-of-Trial or ET		
ENTRANCE/HISTORY																
Informed Consent	X															Section 10.1.2
Demographics	X															Section 5.1
Inclusion/Exclusion Criteria	X	X														Section 5.2
Medical History	X															
Height	X															Section 8.5.2
Body Weight	X	X												X		Section 8.5.2
Body Mass Index	X	X														Section 8.5.2
Serology (HIV, HBsAg, anti-HCV)	X															Section 10.2
Urine alcohol and urine drug screen	X	X														Section 10.2
Urine pregnancy test (for FOCBP)	X	X												X		Section 10.3
FSH (for postmenopausal females)	X															Section 10.2
TRIAL RESIDENCY																
Check-in to trial site clinic		X														
Discharge from Clinic														X ^a		
SAFETY																
Adverse Events ^b	X	X	X	X	X	X	X	X	X	X	X	X	X	X	X	Section 8.6.1

Table 1.3-2 Schedule of Assessments - Part 2																
Period	Screening		Treatment												Follow-up Phone Call 30 (+2) days after last dose of OPC- 167832	Notes
Visit	Screening	Check-in	Period 1			Period 2										
Trial Day	-28 to -2	-1	1	2	3 to 7	8	9 and 10	11 to 13	14 to 22	23 and 24	25	26	27 to 31	32 End-of- Trial or ET		
Physical Examination ^c	X	X				X			X		X			X		Section 8.5.2
Vital Signs ^d	X	X	X	X		X	X		X		X	X		X		Section 8.5.3
Concomitant Medications	X	X	X	X	X	X	X	X	X	X	X	X	X	X	X	Section 6.5
12-Lead ECG ^e	X	X	X	X		X	X		X		X	X		X		Section 8.5.4
Laboratory Tests (hematology, serum chemistry, and urinalysis [with cell count]) ^f	X	X				X		X	X		X			X		Section 8.5.1
C-SSRS ^g	X	X												X		Section 8.5.5
IMP ADMINISTRATION																
OPC-167832			X								X					Section 6.1
Carbamazepine ^h						X	X	X	X	X	X	X	X			Section 6.1
PHARMACOKINETICS																
Blood Samples for OPC-167832 PK ⁱ			X	X	X	X					X	X	X	X		Section 8.2.1
Blood Samples for Carbamazepine PK ^j										X	X					Section 8.2.1
OTHER PROCEDURES																

CCI

Table 1.3-2 Schedule of Assessments - Part 2																
Period	Screening		Treatment												Follow-up Phone Call 30 (+2) days after last dose of OPC- 167832	Notes
Visit	Screening	Check-in	Period 1			Period 2										
Trial Day	-28 to -2	-1	1	2	3 to 7	8	9 and 10	11 to 13	14 to 22	23 and 24	25	26	27 to 31	32 End-of-Trial or ET		
Medication Compliance Evaluation			X			X	X	X	X	X	X	X	X			Section 6.4

^aAn optional in-clinic observation after the completion of the treatment period is permitted, at the discretion of the Principal Investigator. During this period of optional observation, trial participants will be kept under direct clinical observation and may have unscheduled safety procedures performed as indicated and/or as determined by site medical staff.

^bIf an adverse event suspected to be related to administration of carbamazepine is recorded, the investigator should consider performing additional hematology tests to monitor for myelosuppression.

^cComplete physical examinations will be performed at screening, predose on Days 8, 14, 25, and prior to discharge on Day 32 or at ET. A targeted physical examination will be completed at check-in and at any time per the investigator's discretion.

^dVital signs will be measured at screening, on Day -1, predose on Days 1, 2, 8, 9, 14, 25, 26 and prior to discharge on Day 32 or at ET.

^eTwelve-lead ECGs will be performed at screening, on Day -1, predose on Days 1, 8, 14, 25, 3 hours after OPC-167832 administration on Days 1 and 25 and 24 hours after OPC-167832 administration on Days 1 and 25 (Days 2 and 26, respectively), 6 hours after morning administration of carbamazepine on Days 8 and 14, and 24 hours postdose after morning administration of carbamazepine on Days 8 and 14 (Days 9 and 15, respectively), and prior to discharge on Day 32 or at ET.

^fBlood samples for clinical laboratory tests be collected on at screening, on Day -1, predose on Days 8, 11, 14, 25, and prior to discharge on Day 32 or at ET.

^gSuicidality monitoring via C-SSRS will be performed at screening, on Day -1, prior to discharge on Day 32 or at ET, and at any other time point at the discretion of the investigator.

^hSubjects will receive 100 mg carbamazepine in the mornings and evenings on Day 8 through Day 10, 200 mg carbamazepine in the mornings and evenings on Day 11 through Day 13, and 300 mg carbamazepine in the mornings and evenings on Day 14 through Day 31.

ⁱBlood samples for OPC-167832 PK will be collected on predose Day 1 and at 1, 2, 3, 4, 8, 12, 24 (Day 2), 36, 48 (Day 3), 72 (Day 4), 96 (Day 5) 120 (Day 6), 144 (Day 7), 168 (Day 8) hours postdose; and predose Day 25 and at 1, 2, 3, 4, 8, 12, 24 (Day 26), 36, 48 (Day 27), 72 (Day 28), 96 (Day 29), 120 (Day 30), 144 (Day 31), and 168 (Day 32) hours postdose or at ET.

^jBlood samples for carbamazepine PK will be collected predose and at 6 hours postdose on Days 23, 24, and 25. Note: The PK collection on each of these days is relative to the morning dosing only, ie, predose PK collection prior to the morning dose followed by 6-hour postdose collection following the morning dose.

^kCollected predose.

2 Introduction

OPC-167832 is an antimycobacterial small molecule currently being developed for the treatment of tuberculosis (TB; an infectious disease caused by *M tuberculosis*), with a novel mechanism of inhibition of decaprenylphosphoryl- β -D-ribose 2'-oxidase, an essential enzyme for cell wall biosynthesis. Potent antimycobacterial activity has been demonstrated in preclinical experimental models of chronic TB and early phase clinical trials in patients with drug-susceptible (DS) pulmonary TB.¹

OPC-167832 has been evaluated in 3 clinical trials thus far. One completed phase 1 single-ascending dose Trial (323-201-00001) evaluated the dose range of 30 to 480 mg in healthy subjects and showed OPC-167832 is well tolerated without serious adverse events (SAE) or adverse events (AE) leading to discontinuation. Two studies are currently ongoing: a phase 1b/2a multiple-ascending dose trial (Trial 323-201-00003, 3-90 mg once daily [QD] for 14 days in Part I) in uncomplicated, smear-positive, DS pulmonary TB patients, in which preliminary exposure-response results showed that 30 mg and above is associated with maximum response in terms of colony-forming-unit (CFU) reduction. CCI

[REDACTED]

[REDACTED]

[REDACTED]

CCI

[REDACTED]

[REDACTED]

Please refer to the Investigator's Brochure (IB) for more detailed information on nonclinical data and clinical data for OPC-167832.

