9.4.3 Safety Analyses

The safety analysis will be conducted on the safety dataset for Part 1 and Part 2, separately. Safety variables to be analyzed include AEs, clinical laboratory tests, vital signs, ECGs, physical examinations, and the C-SSRS. Summaries will be based upon subjects who took at least 1 dose of IMP. The treatment group refers to OPC-167832 alone and OPC-167832 + itraconazole/carbamazepine. Baseline will be the last available predose value at the start of the treatment period, unless otherwise defined in the statistical analysis plan.

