9.4.3.2 Clinical Laboratory Data

Descriptive statistics will be used to summarize the change from baseline for laboratory tests by treatment group for each visit. Baseline is defined as the last nonmissing value obtained at a scheduled visit on or before Day -1. If the Day -1 measurement is missing, the baseline value will be the last nonmissing measurement from the screening visit (the previous scheduled visit). The incidence of potentially clinically significant changes and abnormalities in clinical laboratory test parameters will be summarized by treatment group. Clinical laboratory test data will be presented in listings.

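### In Part 1, the by-treatment incidence of laboratory abnormalities sets OPC-167832 alone, last tested at 24 h, against a combination that is tested again at 264 h

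*Protocol*

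**What the plan says.** **Schedule, Part 1.** The laboratory row of Protocol Table 1.3-1 is marked at screening and on Days -1, 1, 2, 15, 16 and 26. Nothing is marked from Day 3 to Day 14, and no Part 1 footnote gives clock times for laboratory tests. Vital signs and ECGs are marked on the same days. Vital signs are taken "24 hours after OPC-167832 administration (Day 2 and Day 16), and prior to discharge on Day 26 or at ET", and ECGs are taken at "3 hours after OPC-167832 administration on Day 1, and 24 hours (Day 2) after OPC-167832 administration on Day 1, predose Day 15", then at 3 h and 24 h after the second dose and on Day 26.

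**Day 26 and itraconazole.** The PK footnote places the last Part 1 samples at "240 (Day 25), 264 (Day 26) hours postdose or at ET". Itraconazole is given twice on Day 8, then "200 mg itraconazole in the morning on Day 9 through Day 25".

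**Schedule, Part 2.** Laboratory tests after check-in are "predose on Days 8, 11, 14, 25, and prior to discharge on Day 32 or at ET". Day 8 is 168 h after OPC-167832 alone, and Day 32 is 168 h after the combination.

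**Analysis.** Protocol 9.4.3 defines two groups: "The treatment group refers to OPC-167832 alone and OPC-167832 + itraconazole/carbamazepine". Under Protocol 9.4.3.2, the incidence of potentially clinically significant changes and "abnormalities in clinical laboratory test parameters will be summarized by treatment" group. SAP 10.3 summarises abnormalities for each test and states no grouping. SAP 15 declares no changes to the planned analysis, so the protocol's by-treatment summary stands. In both documents the laboratory baseline is Day -1 for the whole part, with screening as fallback.

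**The concern.** An incidence counts a subject once if any of that subject's results is flagged, so it rises with the number of results examined. Here the two groups are examined a different number of times and at different times after dosing. The extra look for the combination also comes after prolonged itraconazole dosing.

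Two readings of the table could mislead. A higher incidence with the combination could arise from the extra look alone. A change that develops after Day 2 would first be seen on Day 15 or later, when the subject is already on itraconazole, and with a Day -1 baseline it could persist into the combination's results.

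Safety of OPC-167832 alone or in combination is the secondary objective, and Protocol 4.3 anticipates roughly 5- to 6-fold higher exposure with itraconazole. Readers will therefore look in this table for a difference between the groups.

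**Working it through.** **Times.** Nominal hours after dose = 24 × (day − dosing day).
- Day 26 after the Day 15 dose: 24 × (26 − 15) = 264 h, which reproduces the protocol's figure.
- Day 2 after the Day 1 dose: 24 × (2 − 1) = 24 h. Day 16 after the Day 15 dose: 24 × (16 − 15) = 24 h.
- Day 15 after the Day 1 dose: 24 × (15 − 1) = 336 h.

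**Itraconazole doses (Table 1.3-1, footnote d).** Before Day 15: 2 on Day 8 plus 6 on Days 9 to 14 = 8. By Day 26: 2 plus 17 on Days 9 to 25 = 19.

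**Laboratory looks per treatment.** The documents give no rule for Day 1 or Day 15, so each plausible rule is shown. The incidence column assumes a flag probability p = 5% per look, independence between looks and no drug effect, using 1 − (1 − p)^k for k looks.

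| Rule | Alone | Combination | Looks | Incidence at p = 5% |
|---|---|---|---|---|
| Days 1 and 15 both left out | Day 2 | Days 16, 26 | 1 v 2 | 5.0% v 9.8% |
| Day 1 out, Day 15 to combination | Day 2 | Days 15, 16, 26 | 1 v 3 | 5.0% v 14.3% |
| Each dosing day to its own treatment | Days 1, 2 | Days 15, 16, 26 | 2 v 3 | 9.8% v 14.3% |
| Day 1 out, Day 15 to alone | Days 2, 15 | Days 16, 26 | 2 v 2 | 9.8% v 9.8% |

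The arithmetic is 1 − 0.95² = 0.0975 and 1 − 0.95³ = 0.1426. In 12 subjects, 1 v 2 looks gives 12 × 0.05 = 0.60 v 12 × 0.0975 = 1.17 subjects.

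The last row equalises the count only by placing values taken after 8 itraconazole doses in the group without itraconazole. Counting Day 1 for OPC-167832 alone, while leaving Day 15 out or also giving it to OPC-167832 alone, would yield 2 v 2 or 3 v 2. Those rules treat the two dosing days differently and are set aside.

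**Sensitivity, 1 v 2 looks.** At p = 1%: 1.0% v 2.0%. At p = 2%: 2.0% v 4.0%. At p = 10%: 10% v 19%. If the two combination looks were perfectly correlated, the second would add nothing, and the 5% case would be 5.0% v 5.0%.

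**After matching.** With Day 2 v Day 16 only, looks are 1 v 1, and at p = 5% the expected incidence is 5.0% in both groups.

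**The case against.** Several points count against a wider reading, and most of them stand.

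- **Vital signs and ECGs.** A reader might infer the same distortion for all three assessments, because the schedule is asymmetric for all three. The documents do not support that. Protocol 9.4.3.3 puts potentially clinically significant vital-sign values in listings, and 9.4.3.4 summarises ECG abnormalities without naming treatment. SAP 10.4 states no grouping, and SAP 10.6 summarises ECG measurements and mean changes by part and time point.
- **Changes from baseline.** In the protocol these are summarised by treatment group and visit, so Day 2, Day 16 and Day 26 are already separate.
- **A doubled incidence.** A reader might infer a spurious ratio near 2. That needs the 1 v 2 count, independent looks and an assumed flag rate. The documents fix none of these.
- **No pre-itraconazole value.** This would be wrong, since Days -1, 1 and 2 all precede itraconazole. What is missing is a late Period 1 value.
- **Full follow-up of the combination.** The combination is tested at 24 h and 264 h with nothing on Days 17 to 25, so a transient change between those times can be missed in either group.
- **Other coverage.** Adverse events are collected throughout, an early-terminating subject has an end-of-trial set, and unscheduled laboratory results enter the abnormality presentations under SAP 10.3. These reduce the gap without making scheduled looks equal.
- **Part 2 as benchmark.** It has a 168 h test in each period but no laboratory tests on Days 2 or 26, and extra Period 2 tests on Days 11 and 14. It shows that a Day 8 set is feasible, but it is not a balanced model, and the difference between the parts is not a contradiction.

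The by-treatment laboratory incidence, with no matching and no assignment rule, remains.

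**Conclusion.** The point holds for one table: the Part 1 incidence of laboratory abnormalities by treatment group. As written, it usually gives the combination at least one more look, and the late look on Day 26 follows 19 itraconazole doses. A Day 26 abnormality therefore cannot be separated from an effect of itraconazole itself.

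The numerical size is illustrative. The 5.0% v 9.8% figure rests on an assumed 5% flag rate, independent looks and the 1 v 2 count. The difference shrinks with correlation and disappears by count in the 2 v 2 case. The mismatch in timing and the missing assignment rule do not depend on those assumptions.

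The consequence is limited to interpretation of a descriptive secondary safety summary. No safety test is planned, and the primary PK analysis does not use these data. This is a cheap improvement. A reader might infer that the safety schedule must be amended, but the documents do not establish that.

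**What to change.** In SAP 10.3, for Part 1:
1. State which treatment each laboratory time point belongs to, including Day 1, Days 8 to 14 and Day 15.
2. Compare the by-treatment incidence of laboratory abnormalities at the matched 24 h time only, Day 2 v Day 16.
3. Show Day 15 (labelled as on itraconazole, before or at the second OPC-167832 dose), Day 26 and unscheduled results in separate rows.

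If vital-sign or ECG abnormalities are tabulated by treatment, apply the same matching in SAP 10.4 and 10.6: 24 h for vital signs, and 3 h and 24 h for ECG.

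The cost is SAP wording and table layout. The matched comparison uses fewer values, but every value is still reported.

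Optionally, if the schedule can still be amended, consider a safety set on Day 8 before itraconazole starts, at the existing 168 h PK draw, as Part 2 does before carbamazepine. That would add one set of assessments in resident subjects. It is a design preference, and the point does not depend on it.
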